5.3.5.1 Adverse Events Occurring Secondary to Other Events

In general, adverse events occurring secondary to other events (e.g., cascade events or clinical sequelae) should be identified by their primary cause, with the exception of severe or serious secondary events. However, medically significant adverse events occurring secondary to an initiating event that are separated in time should be recorded as independent events on the Adverse Event eCRF. For example:

- If vomiting results in mild dehydration with no additional treatment in a healthy adult, only vomiting should be reported on the eCRF.
- If vomiting results in severe dehydration, both events should be reported separately on the eCRF.
- If a severe gastrointestinal hemorrhage leads to renal failure, both events should be reported separately on the eCRF.
- If dizziness leads to a fall and consequent fracture, all three events should be reported separately on the eCRF.
- If neutropenia is accompanied by an infection, both events should be reported separately on the eCRF.

All adverse events should be recorded separately on the Adverse Event eCRF if it is unclear as to whether the events are associated.

5.3.5.2 Persistent or Recurrent Adverse Events

A persistent adverse event is one that extends continuously, without resolution, between patient evaluation timepoints. The progression (increase and decrease) of an adverse event must be documented in the Adverse Event eCRF.

The initial severity of the event should be recorded, and the severity should be updated to reflect the most extreme severity any time the event worsens. If the event becomes serious, the Adverse Event eCRF should be updated to reflect this.

A recurrent adverse event is one that resolves between patient evaluation timepoints and subsequently recurs. Each recurrence of an adverse event should be recorded separately on the Adverse Event eCRF.

5.3.5.3 Abnormal Laboratory Values

Not every laboratory abnormality qualifies as an adverse event. A laboratory test result must be reported as an adverse event if it meets any of the following criteria:

- Accompanied by clinical symptoms
- Results in a change in study treatment (e.g., dosage modification, treatment interruption, or treatment discontinuation)
- Results in a medical intervention (e.g., potassium supplementation for hypokalemia) or a change in concomitant therapy
- Clinically significant in the investigator's judgment

It is the investigator's responsibility to review all laboratory findings. Medical and scientific judgment should be exercised in deciding whether an isolated laboratory abnormality should be classified as an adverse event.

If a clinically significant laboratory abnormality is a sign of a disease or syndrome (e.g., alkaline phosphatase and bilirubin 5 times the ULN associated with cholestasis), only the diagnosis (i.e., cholestasis) should be recorded on the Adverse Event eCRF.

If a clinically significant laboratory abnormality is not a sign of a disease or syndrome, the abnormality itself should be recorded on the Adverse Event eCRF, along with a descriptor indicating if the test result is above or below the normal range (e.g., "elevated potassium," as opposed to "abnormal potassium"). If the laboratory abnormality can be characterized by a precise clinical term per standard definitions, the clinical term should be recorded as the adverse event. For example, an elevated serum potassium level of 7.0 mEq/L should be recorded as "hyperkalemia."

Observations of the same clinically significant laboratory abnormality from visit to visit should not be repeatedly recorded on the Adverse Event eCRF, unless the etiology changes. The initial severity of the event should be recorded, and the severity or seriousness should be updated any time the event worsens or improves.

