5.1.1.1 Management of Hyperglycemia

Metformin is the first antihyperglycemic medication of choice because of the lower risk of hypoglycemia with this agent. Because metformin in some patients may also cause diarrhea and not be well tolerated, other antihyperglycemic medications such as sulfonylureas (e.g., glimepiride, glipizide) can be used. Extra caution should be used with other drugs such as sulfonylureas because of the increased risk for hypoglycemia with these agents. Consultation with an endocrinologist can be helpful in managing hyperglycemia.

Specific dose modification and management guidelines for hyperglycemia are provided in [Table 2](#).

Table 2 Dose Modification and Management Guidelines for Hyperglycemia (Based on Fasting Blood Glucose)

Grade	Dose Modification and Management Guidelines for Hyperglycemia (based on fasting blood glucose)
Grade 2	Initiation of an anti-hyperglycemic agent (e.g., metformin) and additional glucose monitoring will be implemented. Dosing with GDC-0032/ placebo may either be held or continued per investigator evaluation.
Grade 3 (asymptomatic)	GDC-0032/ placebo dosing will be suspended and the patient will be managed as per standard of care, including implementation of additional glucose monitoring and initiation of, or an increase in, the dose of an anti-hyperglycemic therapy (e.g., metformin). If the hyperglycemic event does not improve to Grade ≤ 1 within 28 days, GDC-0032/ placebo will be permanently discontinued. If the hyperglycemic event improves to Grade ≤ 1 within 28 days, GDC-0032/ placebo dosing may resume at one dose level lower, with approval by the Medical Monitor.

Grade	Dose Modification and Management Guidelines for Hyperglycemia (based on fasting blood glucose)
Grade 3 (symptomatic) ^a , Grade 3 (requiring hospitalization), or Grade 4	GDC-0032/ placebo dosing will be suspended, and the patient will be managed as per standard of care, including implementation of additional glucose monitoring and initiation of, or an increase in, the dose of anti-hyperglycemic therapy. If the hyperglycemic event does not improve to Grade ≤ 1 within 28 days, GDC-0032/ placebo will be permanently discontinued. If the hyperglycemic event improves to Grade ≤ 1 within 28 days, GDC-0032/ placebo dosing may resume at one dose level lower, with approval by the Medical Monitor.

^a For example, blurred vision, frequent urination, excessive thirst.

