5.3.5.4 Abnormal Vital Sign Values

Not every vital sign abnormality qualifies as an adverse event. A vital sign result must be reported as an adverse event if it meets any of the following criteria:

- Accompanied by clinical symptoms
- Results in a change in study treatment (e.g., dosage modification, treatment interruption, or treatment discontinuation)
- Results in a medical intervention or a change in concomitant therapy
- Clinically significant in the investigator's judgment

It is the investigator's responsibility to review all vital sign findings. Medical and scientific judgment should be exercised in deciding whether an isolated vital sign abnormality should be classified as an adverse event.

If a clinically significant vital sign abnormality is a sign of a disease or syndrome (e.g., high blood pressure), only the diagnosis (i.e., hypertension) should be recorded on the Adverse Event eCRF.

Observations of the same clinically significant vital sign abnormality from visit to visit should not be repeatedly recorded on the Adverse Event eCRF, unless the etiology changes. The initial severity of the event should be recorded, and the severity or seriousness should be updated any time the event worsens or improves.

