6.5 SAFETY ANALYSES

Safety analyses will include all patients who received at least one dose of study treatment, with patients allocated to the treatment arm associated with the regimen actually received.

Safety will be assessed through summaries of adverse events, changes in laboratory test results, changes in vital signs, and letrozole and GDC-0032 exposure.

Verbatim descriptions of adverse events will be mapped to thesaurus terms. Adverse event data will be listed by study site, treatment arm, patient number, and study day, severity, relationship to study drug, outcome, and action taken with the study treatments. Events occurring on or after treatment on Day 1 of Week 1 will be summarized by thesaurus term, appropriate thesaurus levels, and NCI CTCAE, v4.0 grade. Serious adverse events, including deaths, will be listed separately and will be summarized.

Relevant laboratory and vital sign (heart rate, blood pressure, and temperature) data will be displayed by time, with NCI CTCAE, v4.0 Grade 3 and 4 values identified, where appropriate. Additionally, all laboratory data will be summarized in tables by NCI CTCAE, v4.0 grade.

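### Sections 5.3.5.3 and 5.3.5.4 have the recorded severity of laboratory and vital-sign adverse events updated on improvement, which conflicts with the most-extreme-severity rule in Section 5.3.5.2 and can lower the stored grade

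*Protocol*

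**What the plan says.** Three neighbouring parts of the protocol govern how the severity of a continuing event is stored.

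- **Section 5.3.5.2 (persistent or recurrent events).** For an event that continues without resolution between evaluations, "the severity should be updated to reflect the most extreme severity any time the event worsens". The eCRF is also to be updated if the event becomes serious. The same section states: "The progression (increase and decrease) of an adverse event must be documented in the Adverse Event eCRF".
- **Section 5.3.5.3 (laboratory values).** "Observations of the same clinically significant laboratory abnormality from visit to visit should not be repeatedly recorded on the Adverse Event eCRF". A change of cause is the one exception. The sentence after it reads: "The initial severity of the event should be recorded, and the severity or seriousness should be updated any time the event worsens or improves".
- **Section 5.3.5.4 (vital signs).** The same bar on repeat entries applies, and again "the severity or seriousness should be updated any time the event worsens or improves".

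Section 6.5 says that adverse events "will be summarized by thesaurus term, appropriate thesaurus levels, and NCI CTCAE, v4.0 grade". Separately, "all laboratory data will be summarized in tables by NCI CTCAE, v4.0 grade". Section 3.4.2 lists the incidence, nature and severity of adverse events first among the safety outcome measures.

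**The concern.** Sections 5.3.5.3 and 5.3.5.4 keep one record per abnormality and let its severity move down as well as up. Section 5.3.5.2 keeps the peak. A site that follows the first rule and a site that follows the second can enter different final grades for the same clinical course.

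At stake is the by-grade adverse event summary, which reports a named safety outcome. A later analysis rule that takes the worst grade per event would not repair this, because it can only use grades still held in the data. If a site had lowered the only severity value on the record, the peak would be absent from the adverse event data. The recording rule therefore has to be right in the protocol itself.

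**Working it through.** The protocol gives no rate or count for this point, so no arithmetic applies. The check sets the rules side by side and follows one event through them.

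**1. Do both rules apply to the same event?** Yes. Section 5.3.5.2 defines a persistent event by its continuing between evaluation timepoints and makes no exception for laboratory or vital-sign events. An abnormality seen at successive visits meets that definition and also falls under 5.3.5.3 or 5.3.5.4.

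**2. Where do the rules differ?**

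| Feature | 5.3.5.2 | 5.3.5.3 and 5.3.5.4 |
|---|---|---|
| Severity on worsening | Raised to the most extreme | Updated |
| Severity on improvement | Severity value kept; decrease to be documented, method not stated | Updated |
| Seriousness | Updated when the event becomes serious | Updated on worsening or improvement |
| Entries per event | Persistent event followed on its record; each recurrence entered separately | No repeat entries from visit to visit unless the etiology changes |

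**3. Trace of an example.** Take asymptomatic Grade 3 hyperglycemia that falls to Grade 1.

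- Table 2 suspends study drug at Grade 3. Under 5.3.5.3 a change in study treatment makes the laboratory result a reportable adverse event, so a record exists.
- Recovery is an expected step. Table 2 makes resumption conditional: "If the hyperglycemic event improves to Grade ≤ 1 within 28 days".
- Under 5.3.5.2 the stored severity stays at Grade 3.
- Under 5.3.5.3, read literally with one severity field, it is updated from Grade 3 to Grade 1, and the Section 6.5 summary would count it as Grade 1.
- Under 5.3.5.3, read as adding a dated grade change, both grades are held and the maximum is still Grade 3.

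**4. What else would capture the peak?**

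- *Laboratory tables by grade (6.5).* These are independent of the adverse event severity field and would show Grade 3 if the result is in the database. Appendix 1 schedules chemistry and glucose at Weeks 1, 5, 9, 13 and 16, and Table 2 adds glucose monitoring from Grade 2 upward. Coverage between visits depends on unscheduled results being entered.
- *Vital signs.* Section 6.5 provides displays over time, with Grade 3 and 4 values identified where appropriate. The by-grade tables are stated for laboratory data only.
- *Expedited reporting (5.2.2, 5.2.3, 5.4.2).* Serious and special-interest events go to the safety department within 24 hours on a separate form. Grade 4 hyperglycemia and symptomatic hyperglycemia of Grade 3 or higher are listed; asymptomatic Grade 3 is not.
- *Audit trail (7.1).* Corrections are retained, but no section makes the trail a source for analysis.

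**5. What remains exposed?** Mainly non-serious Grade 3 laboratory or vital-sign events outside the special-interest list, and then only in the adverse-event-by-grade summary.

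**The case against.** The best defence is that the sections can be read together. Section 5.3.5.2 itself requires decreases to be documented, so an update on improvement may mean no more than adding the grade change that 5.3.5.2 already asks for. No sentence tells sites to erase an earlier grade. The eCRF layout and completion manual are not shown, and how grades are selected for tables is commonly left to the SAP.

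This defence stands against four stronger conclusions that a reader might infer:

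- *That the worst grade is in fact overwritten.* This needs a single overwritable field, which the protocol does not describe.
- *That special-interest or serious cases would be lost.* Reporting starts when the investigator learns of the event and uses a separate form. Later improvement does not withdraw that report, nor does it undo a hospitalization or a life-threatening episode that made the event serious under 5.2.2.
- *That the number of affected patients can be found by applying the Phase I hyperglycemia rates in Section 1.7.1 to this trial.* Those rates come from daily capsule dosing at other dose levels, and they would count possible cases, not misgraded ones.
- *That a bias against detecting toxicity in the active arm has been shown.* The literal rule could only lower a stored grade, but nothing shows how often sites would apply it that way.

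The defence does not remove the conflict. Sections 5.3.5.3 and 5.3.5.4 contain no most-extreme language, and 5.3.5.2 does not say how a decrease is to be entered. Sites could reasonably read the rules differently. Letting seriousness be updated on improvement also has no counterpart in 5.3.5.2.

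**Conclusion.** The point holds as an inconsistency in the recording rules. Sections 5.3.5.3 and 5.3.5.4 conflict with Section 5.3.5.2 for any laboratory or vital-sign event that persists between visits, and their literal wording can lower the stored grade of a recovered event.

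An understated grade in the adverse event summary depends on two conditions: that sites apply the improvement wording literally, and that the form holds one severity value per record. Neither can be confirmed from the protocol. The exposure is narrow, with partial protection from the laboratory tables and expedited reporting, and its size cannot be derived. This is a minor to moderate data-recording defect. It is worth correcting because it touches a stated safety outcome and a worst-grade rule at analysis could not restore a value that sites had lowered.

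**What to change.** Reconcile Sections 5.3.5.3 and 5.3.5.4 with Section 5.3.5.2:

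- Delete the words about improvement from the severity and seriousness sentence in both sections.
- State that the record keeps the initial severity, is raised to the most extreme severity when the event worsens, and keeps seriousness once any criterion has been met.
- State that improvement is entered as a separate dated grade change, or through the event's outcome and resolution date. Section 5.5.1 already requires resolution dates on the Adverse Event eCRF.

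The cost is a wording change in two sections and a matching line in the eCRF completion guidance. If the form does hold a single severity field, the audit trail can be used to check whether any laboratory or vital-sign grades already entered were lowered. No dose, schedule or clinical management rule changes.

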5.3.5.4 Abnormal Vital Sign Values

Not every vital sign abnormality qualifies as an adverse event. A vital sign result must be reported as an adverse event if it meets any of the following criteria:

- Accompanied by clinical symptoms
- Results in a change in study treatment (e.g., dosage modification, treatment interruption, or treatment discontinuation)
- Results in a medical intervention or a change in concomitant therapy
- Clinically significant in the investigator's judgment

It is the investigator's responsibility to review all vital sign findings. Medical and scientific judgment should be exercised in deciding whether an isolated vital sign abnormality should be classified as an adverse event.

If a clinically significant vital sign abnormality is a sign of a disease or syndrome (e.g., high blood pressure), only the diagnosis (i.e., hypertension) should be recorded on the Adverse Event eCRF.

Observations of the same clinically significant vital sign abnormality from visit to visit should not be repeatedly recorded on the Adverse Event eCRF, unless the etiology changes. The initial severity of the event should be recorded, and the severity or seriousness should be updated any time the event worsens or improves.

5.3.5.5 Reporting of Abnormal Liver Function Tests as Hy's Law

The finding of an elevated ALT or AST ($> 3 \times \text{ULN}$) in combination with either an elevated total bilirubin ($> 2 \times \text{ULN}$) or clinical jaundice in the absence of cholestasis or other causes of hyperbilirubinemia is considered to be an indicator of severe liver injury. Therefore, investigators must report as an adverse event the occurrence of either of the following:

- Treatment-emergent ALT or AST $> 3 \times \text{ULN}$ in combination with total bilirubin $> 2 \times \text{ULN}$
- Treatment-emergent ALT or AST $> 3 \times \text{ULN}$ in combination with clinical jaundice

The most appropriate diagnosis or (if a diagnosis cannot be established) the abnormal laboratory values should be recorded on the Adverse Event eCRF (see Section 5.3.5.1) and reported to ABCSG safety department immediately (i.e., no more than 24 hours after learning of the event), either as serious adverse event or an adverse event of special interest (see Section 5.4.2).

5.3.5.6 Deaths

All deaths that occur during the protocol-specified adverse event reporting period (see Section 5.3.1), regardless of relationship to study drug, must be recorded on the Adverse Event eCRF and immediately reported to ABCSG safety department (see Section 5.4.2). This includes death attributed to progression of breast cancer.

Death should be considered an outcome and not a distinct event. The event or condition that caused or contributed to the fatal outcome should be recorded as the single medical concept on the Adverse Event eCRF. Generally, only one such event should be reported. The term "sudden death" should only be used for the occurrence of an abrupt and unexpected death due to presumed cardiac causes in a patient with or without preexisting heart disease, within 1 hour of the onset of acute symptoms or, in the case of an unwitnessed death, within 24 hours after the patient was last seen alive and stable. If the cause of death is unknown and cannot be ascertained at the time of reporting, "unexplained death" should be recorded on the Adverse Event eCRF. If the cause of

death later becomes available (e.g., after autopsy), “unexplained death” should be replaced by the established cause of death.

5.3.5.7 Preexisting Medical Conditions

A preexisting medical condition is one that is present at the screening visit for this study. Such conditions should be recorded on the General Medical History eCRF.

A preexisting medical condition should be recorded as an adverse event only if the frequency, severity, or character of the condition worsens during the study. When recording such events on the Adverse Event eCRF, it is important to convey the concept that the preexisting condition has changed by including applicable descriptors (e.g., “more frequent headaches”).

5.3.5.8 Hospitalization or Prolonged Hospitalization

Any adverse event that results in hospitalization (i.e., in-patient admission to a hospital) or prolonged hospitalization should be documented and reported as a serious adverse event (per the definition of serious adverse event in Section 5.2.2), except as outlined below.

The following hospitalization scenarios are not considered to be adverse events:

- Perform an efficacy measurement for the study
- Hospitalization for respite care
- Planned hospitalization required by the protocol for breast cancer surgery
- Hospitalization for a preexisting condition, provided that all of the following criteria are met:
 - The hospitalization was planned prior to the study or was scheduled during the study when elective surgery became necessary because of the expected normal progression of the disease
 - The patient has not suffered an adverse event
- Hospitalization due solely to progression of the underlying cancer
- Hospitalization for outpatient care outside of normal clinic operating hours that is required per protocol or per local standard of care
- Hospitalization for protocol mandated biopsies

5.3.5.9 Adverse Events Associated with an Overdose

An overdose is the accidental or intentional use of a drug in an amount higher than the dose being studied. An overdose or incorrect administration of study treatment is not itself an adverse event, but it may result in an adverse event. All adverse events associated with an overdose or incorrect administration of study drug should be recorded on the Adverse Event eCRF. If the associated adverse event fulfills serious criteria, the event should be reported to the ABCSG safety department immediately (i.e., no more than 24 hours after learning of the event; see Section 5.4.2).

5.3.5.10 Patient-Reported Outcome Data

Adverse event reports will not be derived from PRO data. However, if any patient responses suggestive of a possible adverse event are identified during site review of the PRO questionnaires, site staff will alert the investigator, who will determine if the criteria for an adverse event have been met and will document the outcome of this assessment in the patient's medical record per site practice. If the event meets the criteria for an adverse event, it will be reported on the Adverse Event eCRF.

5.4 IMMEDIATE REPORTING REQUIREMENTS FROM INVESTIGATOR TO ABCSG

Certain events require immediate reporting to allow ABCSG safety department to take appropriate measures to address potential new risks in a clinical trial. The investigator must report such events to ABCSG safety department immediately; under no circumstances should reporting take place more than 24 hours after the investigator learns of the event. The following is a list of events that the investigator must report to ABCSG safety department within 24 hours after learning of the event, regardless of relationship to study drug:

- Serious adverse events
- Adverse events of special interest (*see Section 5.2.3*)
- Pregnancies

The investigator must report new significant follow-up information for these events to ABCSG safety department immediately (i.e., no more than 24 hours after becoming aware of the information). New significant information includes the following:

- New signs or symptoms or a change in the diagnosis
- Significant new diagnostic test results
- Change in causality based on new information
- Change in the event's outcome, including recovery
- Additional narrative information on the clinical course of the event

Investigators must also comply with local requirements for reporting serious adverse events to the local health authority and IRB/EC.

